Colorectal cancer (CRC) is a malignant tumor originating from the colorectal mucosal epithelium, with rising incidence and mortality rates^[1]. Currently, CRC ranks third in incidence and second in mortality among all cancers worldwide, making it the leading cancer in terms of global incidence and mortality^[2, 3]. According to GLOBOCAN2018, the estimated new cases and deaths from colorectal cancer globally were 1.85 million and 0.88 million respectively, accounting for 28% each in China, and it has become the second most common digestive system cancer and the most prevalent cancer in China. As shown in the "Henan Cancer Registry Annual Report" (2013-2020), colorectal cancer has also been one of the high-incidence malignant tumors threatening the health of the population in our province. Approximately 90% of CRC develops from colorectal polyps, which are considered precancerous lesions of CRC, especially adenomatous polyps^[4, 5]. If removed endoscopically during the polyp stage, 70%-90% of CRC can be prevented^[6]. With the enhancement of people's health awareness, the number of colonoscopies performed annually is increasing. Taking our hospital as an example, the annual growth rate of colonoscopies exceeds 30%, with over 30,000 colonoscopies completed in 2021. However, current colonoscopy examinations have a high miss rate for polyps. Studies have shown that the miss rates for polyps and adenomas after colonoscopy can reach 22%-28% and 12%-26%, respectively^[7]. These missed polyps and adenomas increase the risk of CRC and may be an important cause of interval CRC after colonoscopy, which can account for 0.6% to 9% of all CRC^[8, 9]. A study on the Polish colonoscopy screening program found that the risk of detecting CRC was 10 times higher for those with an adenoma detection rate (ADR) of <20% compared with $\geq 20\%^{[10]}$. Therefore, the ADR is universally recognized as a reliable indicator for measuring colonoscopy quality, and is inversely correlated with the risk of interval CRC^[10, 11]. It can be seen that high-quality colonoscopy and sufficient adenoma detection rate are key to preventing CRC^[12], which can greatly reduce the incidence of colorectal cancer while lowering the miss rate of polyps.

(2) Insufficiencies in the traditional observation method during colonoscopy.

According to the "2014 Chinese Guidelines for Early Screening and Endoscopic Diagnosis and Treatment of Colorectal Cancer", the observation method during colonoscopy starts from the rectum and progresses forward to the cecum, with observations made during withdrawal: from the cecum, ascending colon, transverse colon, descending colon, sigmoid colon to the rectum. Current quality control of colonoscopy mainly focuses on controlling withdrawal time exceeding 6 minutes, controlling cecal intubation rate, and ensuring adenoma detection rate^[13], without specific requirements on the observation method. However, in actual clinical practice, it is found that single withdrawal observation is not enough, as this examination approach is prone to many missed polyps. The likely reason is that the colon is in a compressed state during withdrawal observation. Conventional colonoscopy with two operators used to be widely adopted internationally. Single-operator colonoscopy has become the mainstream insertion method internationally due to its advantages of operational safety, simplicity, high success rate, saving manpower resources and facilitating chromoendoscopy. The core technique of single-operator method is "short-axis reduction", meaning that the colonoscope maintains a straight configuration throughout the examination. The average adult colon length is about 1.5m, but the distance reached during single-operator technique is often between 70-80cm, indicating compression of the colon. In addition, colonic folds become more dense when compressed, making it easier for lesions like polyps to hide within or near folds, leading to misses. Currently in clinical practice of colonoscopy, only withdrawal observation is performed, and only once, on a compressed colon. Many lesions can be easily missed, compromising colonoscopy quality. The sigmoid colon has the most turns in the entire large intestine, and is also the part most prone to compression during colonoscopy insertion. Correspondingly, it is also more prone to misses during withdrawal observation. Although some scholars proposed repeating withdrawal to improve lesion detection rates, observation is still made on a compressed colon regardless of two or three withdrawals. In actual clinical work, many polyps can only be found during advancement. (3) Status of domestic and international studies

Recently, some studies have reported that Endocuff, full-spectrum endoscope examination, water-assisted colonoscopy and repeated examinations, including retroflexion or anteversion, can effectively increase the overall colon ADR^[14-18]. Among these methods, repeated colonic examination may be the simplest and most convenient method for endoscopists, as it does not require additional equipment, personnel or costs. In recent years, domestic and international researchers have done a lot of work on repeated colonoscopy insertion examinations. The most studied is repeated antegrade and retrograde withdrawal observation. A meta-analysis including 6 studies involving 3,901 patients showed^[19]: compared with the normal withdrawal group, the right colon ADR and PDR in the double withdrawal group were significantly higher: ADR (RR [95% CI] 1.39 [1.22,1.58]) and PDR (RR [95% CI] 1.47 [1.30,1.65]), and there was no significant difference in right colon withdrawal time (SMD [95% CI] 1.54 [-0.20,3.28]) or total withdrawal time (SMD [95% CI] 0.37 [-0.39,1.13]) between the two groups. Some studies compare adenoma detection rates of repeated antegrade and retroflexion methods^[20]. A meta-analysis including 4 studies involving 1,882 patients showed that repeated right colon antegrade and retroflexion were both associated with improved ADR, and one of the techniques should be considered to increase ADR and improve colonoscopy quality^[21]. In terms of feasibility, though retroflexion has a higher success rate and lower risk of adverse events, endoscopists are more likely to perform antegrade examinations in routine clinical practice. In addition, some domestic studies have investigated the effect of number of insertions on polyp detection rates. The studies by Feng compared 2 or 3 insertions with 1 insertion and concluded that polyp detection Yan et al. rate with 2 insertions was significantly higher than with 1 insertion. Recently, a domestic study proposed that the focus of observation in different colonic locations during withdrawal and insertion should be different, and the second insertion should focus on locations easily ignored during withdrawal. The results showed that the second insertion method had a higher detection rate for multiple polyps, small polyps, ascending colon polyps, transverse colon polyps, sigmoid colon polyps and sessile polyps (P < 0.05). However, these studies only

3. Objectives

(1) To further explore the impact of a second sigmoid colon insertion on the adenoma detection rate (ADR), analyze factors associated with missed adenomas, and improve clinicians' understanding of the second insertion method;

(2) To further improve the quality of colonoscopy and the early screening positivity rate for colorectal cancer in China.

4. Research Content

(1) Subjects and clinical data

A prospective study was conducted on patients undergoing painless colonoscopy at the First Affiliated Hospital of Zhengzhou University from December 1, 2023 to March 1, 2024 (including outpatients and inpatients). According to the random number table method, patients were divided into two groups: the routine insertion group, where patients underwent a single insertion with observation during withdrawal only; the second insertion group, where after the first withdrawal observation, a second insertion was performed from the rectum through the colonic lumen with deliberate folds advancement in the sigmoid colon, with observation during both insertion and withdrawal. The adenoma detection rate (ADR) and polyp detection rate (PDR) in the sigmoid colon were calculated and compared between the two groups.

(2) Inclusion criteria:

1) Patients who underwent painless colonoscopy at the Gastrointestinal Endoscopy Center of the

First Affiliated Hospital of Zhengzhou University and signed the informed consent for the clinical trial;

2) Aged at age 45 and above with BMI >24.

(3) Exclusion criteria:

1) Patients with contraindications to colonoscopy: patients with acute diverticulitis, patients with known or suspected perforation, patients with severe cardiovascular and cerebrovascular lesions, patients with severe hepatic or renal insufficiency, patients with abdominal aneurysm of large arteries, patients with active hemorrhagic descending colonic lesions, patients with acute radiological colorectal inflammation, patients with advanced carcinomas with pelvic metastases or obvious ascites, patients with severe and extensive intestinal adhesions after abdominal or pelvic surgery;

2) Patients with inflammatory bowel disease, colorectal cancer, familial adenomatous polyposis, Peutz-Jeghers syndrome, abdominal wall hernia, patients with a history of colorectal surgery;

3) Patients with incomplete colonoscopy, i.e., those in whom the endoscopist has failed to successfully cannulate the cecum due to technical difficulties;

4) Patients with poor bowel preparation, i.e., patients with a total score of <6 or any bowel segment of <2 on the Boston Bowel Preparedness Scale score for poor bowel preparation).
(4) Research methods and contents:

1) Preparation for colonoscopy: Routine ECG, infectious disease screening were performed before examination. Patients were advised liquid diet 1 day before and fasted from food and water on the day of examination according to the "Chinese Guidelines for Gastrointestinal Tract Preparation for Endoscopy (2019, Shanghai)". Patients were advised to take oral polyethylene glycol electrolyte powder or sodium phosphate solution for bowel preparation. The last bowel movement should be clear liquid stool before examination.

2) Colonoscopy: All patients took left lateral position with flexed knees close to abdomen. Olympus CF-H290 high definition electronic colonoscope was used under general anesthesia. The endoscopist advanced the colonoscope to the cecum and started withdrawal observation of the colon and rectum mucosa. Polyp lesions found were photographed, removed with biopsy forceps and sent for pathology. When the colonoscope was withdrawn to the rectum after the first examination, patients were randomly allocated to the standard group or second insertion group. Computer-generated randomization numbers divided patients into two groups with allocation information sealed in numbered, opaque envelopes. The endoscopist was blinded to group assignments until completion of first examination of the proximal rectum when the envelope was opened. For the second insertion group, the sigmoid colon was re-inserted with deliberate folds advancement to unfold the folds, and further observations were made during both insertion and withdrawal, polyp lesions found were photographed, removed and sent for pathology. Withdrawal to the anus was then performed in standard manner. The standard group had standard withdrawal observation from rectum to anus for polyp detection and removal.

3) Collection of patient data:

General information: height, weight, gender, age, smoking, drinking, abdominal circumference, hypertension, diabetes, family history of colorectal cancer etc.

Special data: number, location, morphology (pedunculated, sessile), size (<5mm,

5-10mm, >10mm) of polyps, pathology of polyps (inflammatory, hyperplastic, adenomatous); BBPS score for bowel cleanliness; time of first withdrawal, second sigmoid insertion, withdrawal (excluding time for polyp biopsy or treatment); vital signs like blood pressure, heart rate, oxygen saturation (recorded every 5 minutes) of patients during colonoscopy; adverse reactions after procedure (abdominal pain, bloating, nausea, vomiting).

4) Calculation and analysis of data:

(1) Separately calculate and compare the ADR of sigmoid colon between standard and second insertion groups: ADR= number of patients with detected sigmoid adenoma / total number of patients in each group.

(2) Separately calculate and compare the PDR of sigmoid colon between standard and second insertion groups: PDR= number of patients with detected sigmoid polyps / total number of patients in each group

(3) Calculate and compare the postoperative adverse reaction rate between two groups: Adverse reaction rate= number of patients with adverse reactions / total number of patients in each group. 5) Statistical methods: Analysis was performed using SPSS 26.0 software. Counting data were expressed as cases (n) and percentage (%), inter-group comparison was performed using χ^2 test, χ^2 correction or Fisher's exact test. Measurement data were expressed as Mean ± SD, inter-group comparison was performed using t test, t' test or non-parametric test (U test). P <0.05 was considered statistically significant.

5. Expected research outcomes

(1) Analyze the impact of a second sigmoid colon insertion on the adenoma detection rate (ADR) and related risk factors for missed adenomas, thereby improving clinicians' understanding of the second insertion method;

(2) Publish 1 sci paper.

6. Other ethical issues

(1) Privacy protection: Patient data collected will only be used for this study. Personal information of patients collected during the study will be kept confidential. For example, patients' clinical data will be identified by study code number instead of name; information that can identify patient identity will not be disclosed to research group members unless with patient permission; all research members and applicant are required to keep patient identity confidential; patient files will be kept in file cabinets for access by researchers only; government management departments or ethics committees may access personal patient data according to regulations to ensure study is conducted properly; no personal patient information will be disclosed when publishing study results.

(2) Informed consent: All subjects participating in the experiment will be fully informed of risks and benefits and sign an informed consent form.

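### The endoscopist is not among the listed data and the sigmoid ADR test is crude; if several endoscopists take part, a little precision and all operator-level information are lost

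*Combined protocol and SAP*

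**What the plan says.** - **Allocation.** Section 4(1) says "According to the random number table method, patients were divided into two groups". Section 4(4), item 2 (Colonoscopy) says "Computer-generated randomization numbers divided patients into two groups with allocation information sealed in numbered, opaque envelopes". Neither names a stratum, a block or a set of envelopes per operator.
- **Operator.** Item 2 refers to one unnamed role: "The endoscopist was blinded to group assignments until completion of first examination of the proximal rectum when the envelope was opened". The number and experience of the endoscopists are not given.
- **Data collected.** Item 3 lists "General information: height, weight, gender, age, smoking, drinking, abdominal circumference, hypertension, diabetes, family history of colorectal cancer etc". The list is open-ended, but every named item describes the patient. The special data cover polyp features and pathology, then "BBPS score for bowel cleanliness; time of first withdrawal, second sigmoid insertion, withdrawal (excluding time for polyp biopsy or treatment", vital signs and adverse reactions. The endoscopist appears in neither list.
- **Analysis.** Item 5 (Statistical methods) says "Counting data were expressed as cases (n) and percentage", compared by chi-square, corrected chi-square or Fisher's exact test at P < 0.05. There is no stratified test or model.
- **Why the operator is relevant.** The background says "the ADR is universally recognized as a reliable indicator for measuring colonoscopy quality". Section 3 (Objectives) includes an analysis of factors associated with missed adenomas.

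**The concern.** If ADR measures how well an examination is done, it should be expected to differ between the people who do it. The manoeuvre under test is also a matter of operator technique: the sigmoid is entered without shortening, and the folds are deliberately opened.

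If several endoscopists take part, two things follow. First, differences between operators stay in the error of the crude comparison, and chance differences in who examined which arm move the estimate slightly. Second, and more important, a dataset without an operator code cannot treat the endoscopist as a candidate factor for missed adenomas. Nor can it show whether a gain is general or comes from one or two people. What the second insertion finds is what the first withdrawal missed, and that depends partly on who did the first withdrawal.

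**Working it through.** The plan gives no sample size, power, expected ADR or effect size, so it has no figure to reproduce. All values below are assumptions, with 1:1 allocation and a two-sided 0.05 level.

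**1. Share of outcome variance due to the operator.** Share = SD_op² / [p(1 − p)], where SD_op is the between-operator SD of ADR.
- p = 20%, SD_op = 5 points: 0.0025 / 0.16 = 1.56%.
- p = 20%, SD_op = 8 points: 0.0064 / 0.16 = 4.0%.
- Over ADR 10-30% and SD_op 3-10 points (kept plausible for each ADR), the share is about 0.4% to 8%.

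**2. Sample size that adjustment would save.** For 20% v 30%, 80% power:

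n = [1.96√(2 × 0.25 × 0.75) + 0.8416√(0.20 × 0.80 + 0.30 × 0.70)]² / 0.10² = (1.200 + 0.512)² / 0.01 ≈ 293.1, so 294 per arm.

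Multiply by (1 − share), with p(1 − p) = 0.25 × 0.75 = 0.1875:
- SD_op 3 points: share 0.48%, n = 293
- SD_op 5 points: share 1.33%, n = 291
- SD_op 8 points: share 3.41%, n = 284

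At a fixed 294 per arm, power goes from 80.1% to 80.3%, 80.6% and 81.5%. Over four pairs of rates (10 v 15, 15 v 22, 20 v 28 and 20 v 30%) the gain is about 0.2 to 2.3 points.

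**3. Simulated power, 1,000 per arm.** Ten operators of unequal volume, normal operator effects on the logit, marginal ADR 15% v 20%, 20,000 runs per cell (standard error √(0.84 × 0.16 / 20,000) ≈ 0.3 points):

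| Operator logit SD | Crude test | Stratified test, simple randomisation | Stratified test and stratified envelopes |
|---|---|---|---|
| 0.3 | 83.9% | 84.0% | 84.4% |
| 0.5 | 83.5% | 84.6% | 84.7% |
| 0.8 | 83.2% | 85.7% | 85.9% |

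Stratifying the test alone gains 0.1, 1.1 and 2.5 points. Stratifying the envelopes as well adds a further 0.4, 0.1 and 0.2 points.

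At 500 per arm, in a separate set of 20,000 runs per cell, the crude test had 55.2, 55.0 and 55.2% power. With both test and envelopes stratified, power was 54.8, 56.2 and 58.7%. The changes are −0.4, +1.2 and +3.5 points; each figure has a standard error of √(0.55 × 0.45 / 20,000) ≈ 0.35 points.

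**4. Validity of the crude test.** A simulation with 4 or 8 operators, SD_op 5-8 points and 200 to 1,000 patients in total gave type I error of 0.043-0.056 for the crude test and 0.045-0.056 for the stratified one.

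**5. Chance imbalance.** The SD of the difference in expected ADR due to operator mix is roughly SD_op × √(2/n per arm). With SD_op 5 points and 294 per arm: 5 × √(2/294) ≈ 0.41 points, which agrees with the simulated 0.41-0.42. In the ten-operator setting at 500 per arm it is about 0.2-0.6 points. The standard error of the ADR difference there is √(0.15 × 0.85/500 + 0.20 × 0.80/500) ≈ 2.4 points. The imbalance is therefore (0.2/2.4)² to (0.6/2.4)², or about 1% to 6%, of the variance. In a small trial it is larger in absolute terms: with 200 patients in total, its 95th percentile is about 1.4-2.3 points for SD_op 5-8 points.

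**The case against.** **There may be only one endoscopist.** The wording is singular, recruitment lasts three months, and the figure of over 30,000 colonoscopies in 2021 is for the hospital, not the trial. This stands as a limit: several operators is plausible but not stated. With one operator the precision argument disappears, but the plan should then say so, because the result would rest on one person's technique.

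**Individual randomisation already protects the comparison.** This stands in full. A reader might infer that the ADR comparison is biased or its P value invalid. The documents do not support that: patients are randomised individually, the endoscopist is blinded through the first withdrawal, and chance imbalance is already part of the test's error.

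**The power gain is negligible.** Largely true. A reader might expect operator variation to cost the crude test a large amount of power. Even at logit SD 0.8 it keeps about 83% at 1,000 per arm, against about 86% when stratified.

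**Operator identity might be recoverable from hospital records.** Possibly, but the documents do not say so. The claim is therefore limited to the dataset as planned.

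**Stratify the envelopes too.** This is tempting, but the gain beyond the stratified test is under about 1 point. An operator who sees each allocation once the envelope is opened could more easily guess the next one from a personal blocked stack. That would weaken the blinding of the first withdrawal. Nor do the documents say that all operators share one sequence; they only describe no sequence per operator.

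**Conclusion.** The point holds as a minor improvement. The endoscopist is not listed for recording and the main ADR test is crude, in a plan that treats ADR as a quality measure and sets out to study missed adenomas. If there are several endoscopists, the loss of precision is about 0-3 power points under the values assumed above, and type I error stays nominal. The loss of information matters more and does not depend on those values: without a code, the planned dataset can show neither operator as a factor nor the effect by operator. How much chance imbalance matters cannot be settled, because no sample size is given.

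**What to change.** - State in section 4(4), item 2 how many endoscopists take part.
- Add a coded endoscopist ID for each patient to the data list in item 3.
- If there are several, make the main sigmoid ADR comparison in item 5 a Mantel-Haenszel test, or a logistic model, stratified by endoscopist. Show the group difference by endoscopist descriptively, without a significance test for each operator. Include the code among the candidate factors in the analysis of missed adenomas.
- Leave the envelopes as they are.

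The cost is one data field and a sentence or two in the analysis section. Very low-volume operators may need pooling, by a rule fixed before outcome data are seen. The change does not touch allocation, so it can still be made after enrolment has begun, provided the code can be obtained for patients already examined.

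### The only adverse event comparison named is one pooled rate built on four minor symptoms; perforation, bleeding and anaesthesia-related events should be recorded and reported separately by arm

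*Combined protocol and SAP*

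**What the plan says.** Section 4(4), item 3) (Collection of patient data) lists for recording "adverse reactions after procedure (abdominal pain, bloating, nausea, vomiting" and, separately, "vital signs like blood pressure, heart rate, oxygen saturation (recorded every 5 minutes) of patients during colonoscopy".

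Item 4)(3) of the same section names one adverse event analysis: "Calculate and compare the postoperative adverse reaction rate between two groups". It is defined as "Adverse reaction rate= number of patients with adverse reactions / total number of patients in each group". There is no split by type or seriousness, and no end to the period over which reactions are counted.

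Under Colonoscopy (item 2)), the arms separate when the envelope is opened at the rectum. In the second insertion arm the sigmoid colon is re-entered by pushing deliberately into the folds, and "further observations were made during both insertion and withdrawal, polyp lesions found were photographed, removed and sent for pathology". For the other arm: "The standard group had standard withdrawal observation from rectum to anus for polyp detection and removal". All patients are under general anaesthesia.

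Perforation is mentioned once, as an exclusion criterion in section 4(3): "patients with known or suspected perforation". Bleeding is likewise mentioned only there, as an active haemorrhagic lesion of the descending colon. Neither is named as an outcome.

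**The concern.** The randomised difference between the arms is an additional manoeuvre in the sigmoid colon plus any polyp removal that follows from it. A reader of the trial report will want to know whether that step brought any serious harm. The plan as written gives no clear answer under either reading of its symptom list:

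- **List closed.** A perforation, bleed or anaesthesia-related event is counted only if the patient also had pain, bloating, nausea or vomiting.
- **List illustrative.** The event is counted, but in the planned comparison it adds one patient to the same numerator as bloating.

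At stake is the harm half of the result. The ADR and PDR comparisons do not depend on it.

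**Working it through.** **Plan's own figure.** There is none to reproduce. The documents give no sample size, adverse reaction rate or safety margin. Every input below is therefore an assumption, except the 0.05 significance level and the choice of tests, which come from the Statistical methods paragraph. Two-sided testing is also assumed, because the plan does not state it.

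**Assumed inputs.** n = 200, 400 or 800 per arm; r = serious-event rate in the second insertion arm, with none in controls; s = background rate of the four symptoms in both arms; f = share of serious events that enter the pooled rate (f = 1 if the list is illustrative, lower if it is closed and some events carry no listed symptom).

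**Step 1. How far the pooled rate moves.** A serious event changes the numerator only if it is counted and the patient was not already counted for a symptom, so the shift is r × f × (1 − s). Example: 0.01 × 1 × 0.95 = 0.0095, that is 5.00% to 5.95%. With f = 0 the shift is zero whatever the value of r.

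**Step 2. Chance that the pooled comparison gives P<0.05** (uncorrected two-proportion test):

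| r | f | s | Shift (points) | n=200 | n=400 | n=800 |
|---|---|---|---|---|---|---|
| 0.1% | 1 | 5% | 0.095 | 5% | 5% | 5% |
| 0.5% | 0.5 | 10% | 0.225 | 5% | 5% | 5% |
| 0.5% | 1 | 5% | 0.475 | 6% | 6% | 7% |
| 1% | 1 | 30% | 0.70 | 5% | 6% | 6% |
| 1% | 1 | 5% | 0.95 | 7% | 9% | 13% |
| 2% | 1 | 5% | 1.90 | 13% | 21% | 36% |

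Up to r = 0.5% the test barely exceeds its 5% false-positive rate.

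**Step 3. Would testing serious events alone rescue this?** Against zero in controls, Fisher's test needs 6 events at each of the three sample sizes (P = 0.03; 5 v 0 gives P = 0.06). P(X ≥ 6), with X binomial(n, r), is 0.1%, 1.6% and 21% at r = 0.5%, and 1.6%, 21% and 81% at r = 1%. A separate test is not a dependable alternative.

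**Step 4. What separate reporting does give.** The chance of at least one event is 1 − (1 − r)^n. At r = 0.5% this is 63%, 87% and 98%; at r = 0.1% it is 18%, 33% and 55%. Take 400 per arm, 10% background (40 patients per arm) and two serious events in the second insertion arm, one with a listed symptom. On the closed reading the plan reports 41 v 40 patients (10.25% v 10.0%). A separate row shows 2 v 0, a risk difference of 0.5 points with a score-ordered exact 95% CI of about −0.5 to 1.8 points.

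**Step 5. Less favourable assumption: events in controls too.** Both arms have a full colonoscopy, polyp removal and general anaesthesia, so zero in controls is a best case. With X2 ~ binomial(n, 1.0%) and X1 ~ binomial(n, 0.5%), P(X2 ≤ X1), meaning no visible excess, is 39%, 27% and 15% at n = 200, 400 and 800. At 0.5% v 0.25% it is 53%, 39% and 27%.

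**Step 6. Choice of interval.** At 4 v 0 with 400 per arm, the score-ordered exact CI for the risk difference is about 0.02 to 2.55 points and excludes zero, while Fisher's test gives P = 0.12. Methods can disagree at such counts, so the method has to be named in advance.

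**The case against.** Four points can fairly be made for the plan.

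1. **The data could be shown by type.** Reactions are collected under named symptoms, and counting data are reported as cases and percentages, so a breakdown is open to the authors. This stands: it is the planned between-group rate that pools. A breakdown of four symptoms would still not show a perforation or a bleed.

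2. **Vital signs are safety data.** They are recorded every 5 minutes, and the general rule ("Measurement data were expressed as Mean ± SD, inter-group comparison was performed using t test") could be applied to the readings. This also stands, which is why the point is limited to adverse event comparisons. No event is defined from the readings, and they do not enter the adverse reaction rate.

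3. **The list may not be closed.** The general-information list ends in *etc.* and this one does not, but in a translated document that is weak evidence. A reader might infer that serious events would simply go unrecorded; the text does not settle this. The point does not need it settled, because each reading leaves a gap.

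4. **The gain is small and descriptive.** Steps 3 and 5 confirm this, and safety is not among the stated objectives. That limits the weight of the point but does not remove it, given what the change costs.

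A reader might also infer that the re-insertion is less safe, since the Background credits single-operator colonoscopy with operational safety and then sets short-axis reduction aside for the second insertion. The documents do not support that. The safety remark contrasts one operator with two and is not attributed to short-axis reduction, and nothing says that single-operator technique is given up.

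**Conclusion.** The point holds in limited form. The plan names one pooled adverse reaction rate as its only adverse event comparison, lists only four minor symptoms, and does not name perforation, bleeding or anaesthesia-related events as outcomes. Followed as written, a serious event in the arm with the extra manoeuvre would be left out of that rate or merged into it.

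The size rests wholly on assumed inputs. With 200 to 800 per arm, serious events in up to 1% of the second insertion arm and none in controls, the pooled test detects the excess in at most about 13% of trials. If controls have events too (1.0% v 0.5%), even a separate table shows no excess in 15% to 39% of trials. The benefit is that serious events become visible by arm, not that a difference is proved. Detection-rate results are untouched, and nothing here shows that the second insertion is harmful.

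The opening and consent pages were not available, so any safety wording there could not be checked.

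**What to change.** - Record any adverse event from envelope opening onward, in both arms alike.
- State when capture ends, and do not make the window shorter than the current wording, which counts reactions after the procedure with no end point. The trial enrols inpatients; for them, include events already in the hospital record.
- Report perforation, bleeding, anaesthesia-related events, and unplanned intervention or admission separately from the four symptoms. Give counts by arm with the risk difference and an exact 95% CI whose method is named in advance. Label this as description, not as a powered test.
- Keep the four-symptom rate and its comparison as planned.

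The cost is a few case-report-form fields and one table. The reported adverse event rate may look less favourable than the symptom rate alone. The change concerns recording and reporting only and alters nothing in how patients are managed.
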